##### b. PHARMACOKINETICS

1. Distribution: Nivolumab has linear pharmacokinetics after single and multiple dosing within the range 0.1 mg/kg to 10 mg/kg. The volume distribution (Vd) is 8L.
2. Elimination: Clearance is independent of dose in the range 0.1 mg/kg to 10 mg/kg. The total body clearance is 9.5 mL/hr, and the elimination half-life is approximately 26.7 days. Body weight normalized dosing showed approximately constant trough concentrations over a wide range of body weights.

c. ADVERSE EFFECTS

1. **Adverse Effects:** The Comprehensive Adverse Events and Potential Risks list (CAEPR) provides a single list of reported and/or potential adverse events (AE) associated with an agent using a uniform presentation of events by body system. In addition to the comprehensive list, a subset, the Specific Protocol Exceptions to Expedited Reporting (SPEER), appears in a separate column and is identified with bold and italicized text. This subset of AEs (SPEER) is a list of events that are protocol specific exceptions to expedited reporting to NCI (except as noted below). Refer to the 'CTEP, NCI Guidelines: Adverse Event Reporting Requirements' [http://ctep.cancer.gov/protocolDevelopment/electronic\\_applications/docs/aeguidelines.pdf](http://ctep.cancer.gov/protocolDevelopment/electronic_applications/docs/aeguidelines.pdf) for further clarification. *Frequency is provided based on 2069 patients.* Below is the CAEPR for Nivolumab.

**NOTE:** Report AEs on the SPEER **ONLY IF** they exceed the grade noted in parentheses next to the AE in the SPEER. If this CAEPR is part of a combination protocol using multiple investigational agents and has an AE listed on different SPEERs, use the lower of the grades to determine if expedited reporting is required.

Version 2.5, June 10, 2023

Adverse Events with Possible Relationship to Nivolumab (CTCAE 5.0 Term) [n= 2069]			Specific Protocol Exceptions to Expedited Reporting (SPEER)
Likely (>20%)	Less Likely (<=20%)	Rare but Serious (<3%)	
BLOOD AND LYMPHATIC SYSTEM DISORDERS			
	Anemia		Anemia (Gr 3)
		Blood and lymphatic system disorders – Other (lymphatic dysfunction)	
CARDIAC DISORDERS			
		Cardiac disorders – Other (cardiomyopathy)	
		Myocarditis	
		Pericardial tamponade 	
		Pericarditis	
ENDOCRINE DISORDERS			
	Adrenal insufficiency 		
	Hyperthyroidism 		
	Hypophysitis 		
	Hypothyroidism 		
EYE DISORDERS			
		Blurred vision	
		Dry eye	

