 Nivolumab being a member of class of agents involved in the inhibition of "immune checkpoints", may result in severe and possibly fatal immune-mediated adverse events probably due to T-cell activation and proliferation. This may result in autoimmune disorders that can include (but are not limited to) autoimmune hemolytic anemia, acquired anti-factor VIII immune response, autoimmune aseptic meningitis, autoimmune hepatitis, autoimmune nephritis, autoimmune neuropathy, autoimmune thyroiditis, bullous pemphigoid, exacerbation of Churg-Strauss Syndrome, drug rash with eosinophilia systemic symptoms [DRESS] syndrome, facial nerve disorder (facial nerve paralysis), limbic encephalitis, hepatic failure, pure red cell aplasia, pancreatitis, ulcerative and hemorrhagic colitis, endocrine disorders (e.g., autoimmune thyroiditis, hyperthyroidism, hypothyroidism, autoimmune hypophysitis/hypopituitarism, thyrotoxicosis, and adrenal insufficiency),

sarcoid granuloma, myasthenia gravis, polymyositis, and Guillain-Barre syndrome.

- 4 Pancreatitis may result in increased serum amylase and/or more frequently lipase.
- 5 Cytokine release syndrome may manifest as hemophagocytic lymphohistiocytosis with accompanying fever and pancytopenia.
- 6 Complications including hyperacute graft-versus-host disease (GVHD), some fatal, have occurred in patients receiving allo stem cell transplant (SCT) after receiving Nivolumab. These complications may occur despite intervening therapy between receiving Nivolumab and allo-SCT.
- 7 Infusion reactions, including high-grade hypersensitivity reactions which have been observed following administration of nivolumab, may manifest as fever, chills, shakes, itching, rash, hypertension or hypotension, or difficulty breathing during and immediately after administration of nivolumab.

**Adverse events reported on Nivolumab trials, but for which there is insufficient evidence to suggest that there was a reasonable possibility that Nivolumab caused the adverse event:**

**BLOOD AND LYMPHATIC SYSTEM DISORDERS** - Leukocytosis

**CARDIAC DISORDERS** - Atrial fibrillation; Atrioventricular block complete; Heart failure; Ventricular arrhythmia

**EAR AND LABYRINTH DISORDERS** - Vestibular disorder

**EYE DISORDERS** - Eye disorders - Other (iritocyclitis); Optic nerve disorder; Periorbital edema

**GASTROINTESTINAL DISORDERS** - Constipation; Duodenal ulcer; Flatulence; Gastrointestinal disorders - Other (mouth sores); Vomiting

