j. Patients must not have any known uncontrolled intercurrent illness including, but not limited to symptomatic congestive heart failure, unstable angina pectoris, hemodynamically unstable cardiac arrhythmia, or psychiatric illness/social situations that would limit compliance with study requirements.

k. Patients must not have a condition requiring systemic treatment with either corticosteroids ( $>10$  mg daily prednisone equivalents) or other immunosuppressive medications within 14 days prior to registration. Inhaled or topical steroids, and adrenal replacement doses  $>10$  mg daily prednisone equivalents are permitted in the absence of active autoimmune disease. Steroid use for the control of Hodgkin lymphoma symptoms is allowable, but must be discontinued prior to Cycle1, Day1.

l. Patients with peripheral neuropathy must have < Grade 2 at date of registration.

- m. Patients must not have active autoimmune disease that has required systemic treatment in past 2 years (i.e., with use of disease modifying agents, immunosuppressive drugs, or corticosteroids with doses higher than prednisone 10 mg or equivalent). Autoimmune diseases include but are not limited to autoimmune hepatitis, inflammatory bowel disease (including ulcerative colitis and Crohn's disease), as well as symptomatic disease (e.g.: rheumatoid arthritis, systemic progressive sclerosis [scleroderma], systemic lupus erythematosus, autoimmune vasculitis [e.g., Wegener's Granulomatosis]); CNS or motor neuropathy considered of autoimmune origin (e.g., Guillain-Barre Syndrome and Myasthenia Gravis, multiple sclerosis or glomerulonephritis). Vitiligo, alopecia, hypothyroidism on stable doses of thyroid replacement therapy, psoriasis not requiring systemic therapy within the past 2 years are permitted.
- n. No second prior malignancy is allowed except for adequately treated basal (or squamous cell) skin cancer, any in situ cancer or other cancer for which the patient has been disease free for two years.

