## 7.2 Pre-medication, Concomitant Therapy, and Supportive Care Guidelines

- a. Pre-medication: Pre-medications including antiemetics and steroids can be administered per institutional practice.
- b. Concomitant Therapy

1. Required concomitant medications:  
The use of granulocyte-colony stimulating factor (G-CSF) is required for patients receiving BV + AVD. G-CSF is optional for patients receiving N + AVD. See [Section 7.3](#) for G-CSF dose and scheduling.
2. Permitted concomitant medications:  
Dexrazoxane use is allowed concomitant with doxorubicin as a cardiac protectant per investigator choice and must be captured on study CRFs if used. Since there may be an increased risk of typhlitis associated with myelosuppression with the use of dexrazoxane, treating investigators are cautioned that evaluation for typhlitis should be kept in mind for patients presenting with severe abdominal pain.

The use of topical, inhalational and ophthalmic steroids is permitted. Corticosteroids are permitted as part of a chemotherapy premedication regimen per institutional standards. In addition, a brief course of corticosteroids for prophylaxis (e.g.; contrast dye allergy) or for treatment of non-autoimmune conditions (e.g.; delayed-type hypersensitivity reaction caused by contact allergen) is permitted.

Patients may receive hormonal contraceptives.

3. Prohibited concomitant medications:
  - Any investigational agents other than nivolumab.
  - Any concurrent antineoplastic therapy other than AVD, brentuximab vedotin, or nivolumab (i.e.: chemotherapy, hormonal therapy, immunotherapy, radiation therapy except for those subjects planned to receive radiation as specified in [Section 7.5](#)).
  - Immunosuppressive agents (except to treat a drug-related AE).
  - Systemic corticosteroids (defined as equivalent to > 10 mg daily prednisone) except as pre-medications, antiemetics, for prophylaxis, or treatment of non-autoimmune conditions for brief course as noted in preceding section, and as stated in [Section 18.3](#) to treat a drug-related AE).
  - Replacement therapy (e.g., thyroxine, insulin, or physiologic corticosteroid replacement therapy for adrenal or pituitary insufficiency, etc.) is not considered a form of systemic treatment. Short-term steroid premedication for contrast allergy is also permitted.
  - Use of ritonavir or HIV therapy that uses pharmacologic boosters, such as cobicistat in the control arm for HIV+ patients or HIV, is prohibited.

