**Patient Preparation**

Patients must fast for at least four hours before the PET-CT scan. Oral hydration is strongly encouraged prior to and during injection of  $^{18}\text{F}$ -FDG (250-500 mL water can be given PO during the uptake period). Intravenous fluids containing dextrose or parenteral feeding should be withheld for at least 6 hours prior to the injection of  $^{18}\text{F}$ -FDG. No steroid administration is allowed for at least 7 days prior to FDG-PET imaging. Active exercise should be discouraged for at least 24 hours prior to the study. Muscle stress, tension, chewing, and movement during the uptake period should be minimized to decrease muscle uptake. Patients should not speak during the injection and uptake period. Interviews with the patient should be withheld until after completion of the imaging study.

The blood glucose level should be checked before  $^{18}\text{F}$ -FDG injection. Blood sugar (measured by glucometer) must be less than 200 mg/dL at the time of the FDG-PET-CT study. If the blood glucose level is greater than 200 mg/dL, the FDG-PET-CT imaging should be rescheduled. If the blood glucose level still exceeds 200 mg/dL on the following scheduled day for PET scanning, the patient will not be included in the analysis. Insulin administration immediately before the PET-CT study to reduce the glucose levels is not allowed. Patients with diabetes should continue to adhere to their oral agents or insulin routines. These medications should not be administered near the  $^{18}\text{F}$ -FDG injection time. In insulin-dependent patients, insulin should be administered at least 5 hours prior to the  $^{18}\text{F}$ -FDG injection. Patients with diabetes who are on diabetic medication should take their medication 4-5 hours prior to the test.

Metallic objects should be removed from the patients whenever possible. Patients should be kept in a warm waiting room prior to  $^{18}\text{F}$ -FDG injection to avoid brown adipose tissue uptake. In anxious and claustrophobic patients, administration of oral diazepam (0.06-0.10 mg/kg) is recommended 30-40 minutes prior to the initiation of the imaging study.

Weight (kg), height (cm), blood glucose (mg/dL), and the date and time of chemotherapy, glucose levels and colony stimulating factor administration (e.g., GCSF, GMCSF) should be recorded prior to the injection of  $^{18}\text{F}$ -FDG.

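### The steroid ban before FDG-PET in Section 18.5b has no exception for permitted adrenal or pituitary replacement, so followed literally it withholds replacement for 7 days before each protocol PET

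*Combined protocol and SAP*

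**What the plan says.** Section 18.5b (Patient Preparation) sets the conditions for FDG-PET-CT. On steroids it says only: "No steroid administration is allowed for at least 7 days prior to FDG-PET imaging". The rule is not tied to a timepoint, so it covers every protocol FDG-PET. On diabetes medication, the same text says the opposite: "Patients with diabetes should continue to adhere to their oral agents or insulin routines".

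Two other sections permit steroid replacement:

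- Section 5.4k (eligibility) allows "Inhaled or topical steroids, and adrenal replacement doses" above 10 mg daily prednisone equivalent, provided there is no active autoimmune disease.
- Section 7.2b.3 (prohibited medications) takes replacement out of the ban on systemic corticosteroids. It lists thyroxine and insulin, and says that "physiologic corticosteroid replacement therapy for adrenal or pituitary insufficiency, etc.) is not considered a form of systemic treatment".

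Section 3.1c lists adrenal insufficiency and hypophysitis among the nivolumab risks, in the column for events seen in at most 20% and not in the rare-but-serious column (under 3%). Both carry footnote 3, which warns that checkpoint inhibition "may result in severe and possibly fatal immune-mediated adverse events probably due to T-cell activation and proliferation" and includes "autoimmune hypophysitis/hypopituitarism, thyrotoxicosis, and adrenal insufficiency" among its endocrine examples.

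**The concern.** The protocol admits and keeps patients who need daily corticosteroid replacement, then gives a scan instruction that they cannot follow while taking it. The wording is mandatory, whereas several neighbouring instructions in Section 18.5b are recommendations. A scheduler or imaging department working from the preparation text alone would tell such a patient to stop.

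What is at stake is the safety of the individual patient. A trial document should not direct anyone to interrupt treatment for adrenal or pituitary insufficiency in order to obtain a response scan.

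**Working it through.** There is no sample-size, power or error-rate figure to reproduce. The check sets the provisions side by side.

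**1. Does Section 18.5 contain an exception?** No. Sections 18.5a to 18.5c give no exemption by dose, route, indication or timepoint, and do not refer to Section 7.2. Exceptions found: 0.

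**2. Does the protocol permit replacement elsewhere?** Yes, in two places: Section 5.4k at entry and Section 7.2b.3 on treatment. Neither refers to PET preparation.

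**3. Does Section 7.2b.3 settle the matter?** Not on its wording. It says that replacement is not systemic treatment, and it qualifies the list of prohibited concomitant medications. Section 18.5b bars steroid administration and does not use the word systemic. A reader can argue from one to the other, but the text does not make the link.

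**4. Did the preparation text need to say it?** Section 18.5b deals expressly with one essential drug class, diabetes medication, and tells patients to continue it. Section 7.2b.3 groups insulin with corticosteroid replacement. Only the first of the two is protected in the scan instructions.

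**5. Do such patients reach the scans?**

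- Patients on replacement at entry may have the baseline PET (Section 5.1c) and the end-of-treatment PET (Section 7.4).
- In Arm 1, Section 8.2c.2 holds nivolumab for Grade 2 or 3 hypophysitis or adrenal insufficiency until it falls below Grade 2. Section 8.2c then resumes full dose.
- After a Grade 4 event nivolumab stops, but AVD may continue. Section 9.1, footnote h, still requires the end-of-treatment PET when treatment ends early.
- Depending on the patient, there may also be an interim PET (Section 7.4b), a post-radiotherapy PET (Section 7.6b) and a PET at progression or before subsequent therapy (Section 7.6c).

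**6. What does literal compliance cost?** At least 7 days without replacement before each FDG-PET that the patient has.

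**7. Does it touch an endpoint?** No. Section 18.5b excludes a patient from analysis for persistently high glucose, but states no consequence for steroid use. Section 7.4 bases response on the local reading, so the scan still counts.

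**The case against.** **The rule plainly aims at pharmacologic steroids.** Section 18.5b is a generic imaging paragraph, Section 7.2b.3 sets replacement apart, and endocrine care is directed to the Section 18.3 algorithm (its figure is not visible in the text available). Most clinicians would scan on replacement. This stands as a prediction of practice, and it is why the point is small. It does not change what the sentence says, and relying on each site to override mandatory wording is a weaker safeguard than one clause.

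**CT or MRI offers another route.** Sections 5.1c, 7.4, 7.6b and 7.6c accept other modalities, but only where PET is contra-indicated. No section says that a preparation requirement counts as a contra-indication. A patient imaged without FDG-PET is outside the rule.

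**Protocol control of the baseline scan is weaker.** This stands. It may be a standard-of-care scan done up to 42 days before registration, before protocol preparation rules are applied.

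Three stronger readings are tempting, and the documents do not support them:

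- A reader might add the 7-day gaps across all scans into a running total. The windows are spread over months, the sum has no stated clinical meaning, and it would include the baseline scan.
- A reader might size the problem by the number of patients with a mandatory interim PET, such as all those aged 12-17. That counts scans required, not patients on replacement.
- A reader might infer that inhaled, topical and ophthalmic steroids need the same exemption. Section 7.2b.2 does say "The use of topical, inhalational and ophthalmic steroids is permitted", but permission as concomitant medication is a different question from scan preparation, and no safety argument for exempting them follows from these documents.

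**Conclusion.** The conflict is real and narrow. Section 18.5b, read as written, withholds for 7 days before each protocol FDG-PET a treatment that Sections 5.4k and 7.2b.3 permit. It is a safety point about wording, optional in rank but worth making.

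Size: few patients. The documents give no rate of adrenal or pituitary insufficiency for N-AVD. Section 2.4b reports endocrinopathy in 26% of the 51-patient nivolumab plus AVD cohort, all of it thyroid-related, so no adrenal or pituitary case is reported there. The 20% bound in Section 3.1c is a column ceiling and not an estimate. I therefore give no count.

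The conclusion rests on two assumptions. The first is that the patient actually has an FDG-PET. The second is the clinical premise that needed replacement should not be interrupted for a scan. Footnote 3 of Section 3.1c shows how seriously the underlying conditions are taken, but the documents do not quantify the harm of a 7-day gap.

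A reader might infer from the preparation breach that responses or progression dates become unreliable. Nothing in the documents supports that. Steroid courses for adverse events are a separate matter and are not covered here.

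**What to change.** Extend the single sentence in Section 18.5b so that it reads: "No steroid administration is allowed for at least 7 days prior to FDG-PET imaging", *except physiologic adrenal or pituitary replacement, which must not be stopped for the scan*. The exception should apply to all protocol FDG-PETs. This agrees with Sections 5.4k and 7.2b.3, and nothing else in the preparation text need change.

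The cost is one clause, with no new visit, scan, form item or analysis. It is still a protocol change that needs IRB approval and site activation, so the sensible course is to include it in the next revision made for other reasons. The remaining benefit falls with time. Section 18.13 records 400 patients with banked end-of-treatment samples by 15 May 2022, so many scheduled PETs are already past. It still applies to scans yet to be done, including those at progression.

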## 18.6 Radiation Therapy Guidelines

End of treatment Residual PET RT may be administered at the discretion of the treating physician, provided that the intent to deliver RT was declared at study enrollment and the criteria in [Section 7.5](#) are met.

Timing of protocol therapy administration, response assessment studies, and surgical interventions are based on schedules derived from the experimental design or on established standards of care. Minor unavoidable departures (up to 72 hours) from protocol directed therapy and/or disease evaluations (and up to 1 week for surgery) for valid clinical, patient and family logistical, or facility, procedure and/or anesthesia scheduling issues are acceptable (except where explicitly prohibited within the protocol).

**Radiotherapy (RT) for patients can only be delivered at approved RT facilities.**

**Pre-treatment Review of Radiation therapy plans will be conducted by IROC Rhode Island. Data detailed in [Section 14.4](#) must be submitted one week prior to the start of Radiation Therapy for review and approval. This RT QA review will also confirm sites of partial response which will require radiation. Any radiation therapy delivered not consistent with the RT QA review response categorization will be considered a major protocol deviation.**

### a. Indications for Radiotherapy

The indication for RT will be based on imaging evaluation performed upon completion of 6 cycles of systemic therapy. In general terms, RT will be delivered when patients have 1-2 sites initially involved with HL that achieve only a partial response. Specifically, RT will be indicated when the patient has persistent sites upon completion of 6 cycles of systemic therapy that meet all of the following criteria:

1. Residual nodal mass  $\geq 2.5\text{cm}$  in axial diameter, or residual extranodal lesion  $>1\text{cm}$  in axial diameter (e.g. lung nodule or splenic nodule), and
2. Has Deauville score = 4 or 5, and
3. Has  $\geq 30\%$  reduction in maximal transverse diameter compared to pre-treatment imaging.

RT may be given to one or two nodal sites.

The following circumstances are contraindications for RT:

1. Deauville score 5 due to development of new PET avid sites during systemic therapy.
2. Three or more persistent PET-avid (Deauville score 4-5) sites at completion of systemic therapy.
3. A PET-avid site contained within a CT abnormality that has not achieved at least 30% reduction in transverse diameter.

Patients with these features are unlikely to be cured with RT, and biopsy with alternative management should be considered.

b. Radiotherapy Dose and Schedule

**PET Positive After 6 Cycles of Systemic Therapy (PET score 4-5)**

Radiotherapy will consist of 3000-3600 cGy in fractions of 150-200 cGy per day. The treatment will be given 5 days per week. All fields should be treated once each day. The total elapsed treatment time will be approximately 4 weeks.

c. Timing of Radiotherapy and Starting Criteria

Treatment should begin 5-12 weeks from Cycle 6, Day 15 of chemotherapy or when blood counts have recovered.

Criteria include an ANC > 750/ $\mu$ L and platelets > 75,000/ $\mu$ L prior to treatment for each site.

d. Credentialing Requirements

Patients may receive RT with photons or proton therapy. Intensity Modulated Radiation Therapy (IMRT), VMAT (or its equivalents) or protons are allowed in circumstances where the treating oncologist believes these provide significant clinical benefits compared to conventional anterior-posterior parallel opposed pairs. Investigators may use proton therapy only if their institution has been appropriately credentialed by the IROC Houston QA Center. Credentialing requirements for proton therapy which include, but are not limited to, completion of a proton facility questionnaire, a successful IROC Houston site visit, which identifies the proton technique(s) which can be used, annual monitoring of the proton beam calibration, e.g. IROC Houston's monitoring program, and successful digital phantom data submission to IROC Houston (details for data submission are available at <http://rpc.mdanderson.org>). Centers not previously credentialed for use of proton therapy treatment of thoracic tumors must irradiate the Proton Lung Phantom available from IROC Houston.

The credentialing requirements by treatment modality are summarized in the following table.

RT Credentialing Requirements	Web Link for Credentialing Procedures and Instructions http://irochouston.mdanderson.org			
	Treatment Modality			Key Information
	3D- CRT	Photon	Proton	
Facility Questionnaire	X	X	X	The IROC Houston electronic facility questionnaire (FQ) should be completed or updated with the most recent information about your institution. To access this FQ, email [contact] to receive your FQ link.
Credentialing Status Inquiry Form	X	X	X	To determine if your institution has completed the requirements above, please complete a "Credentialing Status Inquiry Form" found under Credentialing on the IROC Houston QA Center website ( http://irochouston.mdanderson.org ).
Phantom Irradiation		X	X	Sites treating with IMRT and not previously credentialed for its use on COG trials must irradiate IROC Houston's thoracic phantom. Proton centers must complete all required phantom irradiations for IROC Houston credentialing, including the proton lung phantom. Instructions for requesting and irradiating the phantoms are found on the IROC Houston web site. ( http://irochouston.mdanderson.org ).
Motion Management (when used)		X	X	If treating with IMRT and gating or tracking methods are used to compensate for respiratory motion, IROC Houston's Lung Phantom must be irradiated with its accompanying reciprocating platform to simulate motion. Instructions for requesting and irradiating the phantom are found on the IROC Houston web site. ( http://irochouston.mdanderson.org )
Credentialing Notification Issued to:				
Institution				Institution will be credentialed for the treatment modality that they intend to use on all patients. IROC Houston QA Center will notify the institution that all desired credentialing requirements have been met.

e. Equipment

1. Modality

Photons with a nominal energy of  $\geq 4$  MV and  $\leq 18$  MV are preferred. In the unusual circumstance of an isolated superficial lesion, electron fields may be used. Conventional, conformal, and IMRT techniques are allowed in this study. Patients receiving IMRT should have this delivered with 6 MV photon beams, and 18 MV photon beams should not be used to deliver IMRT.

Proton therapy may be delivered using passively scattered proton or scanning beams provided that the specific beam line in use has been appropriately credentialed. Selected proton energies should be high enough to adequately provide target coverage. Range shifters may be used to make fine adjustment to the maximum proton range.

Use of IMRT in conjunction with gating or tracking techniques requires credentialing by the IROC Houston. The Motion Management Reporting Form shall be submitted with the Quality Assurance Documentation materials whenever motion management techniques are used.

2. Guidelines and Requirements for the Use of Proton Beam Therapy

Investigators using proton beam therapy will be required to comply with current guidelines for the use of protons in National Cancer Institute sponsored cooperative group trials. These guidelines are available on the IROC Houston website at <http://irochouston.mdanderson.org>. Questions regarding proton therapy on trial should be sent to [name] MD ([[contact]](mailto:[contact])) and/or [name] PhD ([[contact]](mailto:[contact])). These guidelines specify the following for the participating institution: dose reporting will be in Cobalt Gy equivalent (1 CGE = 1 proton Gy \* 1.1) which is the same as ICRU 78 DRBE; radiation doses shall be prescribed to protocol specified definitions for gross (GTV) and clinical (CTV). For CT number to proton stopping power calibration uncertainties, set-up uncertainties and target motion, additional margin, smearing, range of modulation will be added on a per beam basis for passive scattering and uniform scanning. The proton institution is required to participate in on-site and remote review according to COG requirements.

3. Treatment Planning

CT (volumetric) based planning is required to optimize dose to the targeted volume while documenting dose to normal tissues. Slices  $\leq 5$  mm thick should be taken throughout the extent of the irradiated volume.

In cases where the mediastinum or spleen is being treated, the entire thoracic volume should be scanned to create accurate estimates of lung and heart dose.

There are mandatory requirements for submission of the dose to selected normal tissues (see [Section 18.6I](#)). A Dose Volume Histogram (DVH) is necessary to determine target coverage and evaluate dose to normal tissues.

4. In-Room Verification of Spatial Positioning

Image guidance to verify patient position is an important standard feature of contemporary RT delivery. Institutional protocols should be in place common to verify patient position. Orthogonal pair (AP and lateral) portal images (MV or kV) or cone-beam imaging are acceptable. There is no central review of verification imaging.

f. Target Volumes

Recommendations of The International Commission on Radiation Units and Measurements (ICRU) for prescription methods and nomenclature will be utilized for this study (Reports 50, 62, and 78).

It is not necessary to treat initially involved sites that have achieved an anatomic and metabolic Complete Response. The indications for RT are outlined in [Section 18.6a](#) and should be the principal determinants in defining the gross tumor volume (GTV), the clinical target volume (CTV) and the planning target volume (PTV).

Note: The following definitions apply only to sites of disease that meet the criteria for receiving RT.

1. Post-Chemotherapy GTVtotal

Following completion of 6 cycles of systemic therapy, the post-chemotherapy GTVtotal includes persisting imaging abnormalities seen on CT that encompass a PET-avid site (Deauville 4-5). Note that for RT planning purposes, this includes the parts of that mass that are PET-negative. The GTV (and CTV) are not just the PET-avid volume within the persistent CT abnormality. Residual nodal masses must be  $\geq 2.5$  cm in greatest axial diameter and residual extranodal lesions (lung nodules, splenic nodules) must be  $\geq 1$  cm to be eligible for RT. The CTV and PTV encompassing the GTVtotal are to be prescribed 30Gy.

GTVPET+: This is defined as the volume of imaging abnormality that remains PET avid (Deauville score 4-5) following completion of 6 cycles of systemic therapy. This volume is contained within, and is typically smaller than, the post-chemotherapy GTVtotal defined above. This volume, and its surrounding PTV, should be boosted with an additional 6Gy (total 36Gy) provided the boost does not cause the normal tissue dose limits described below to be exceeded. The boost is not required if it causes the normal tissue constraints to be exceeded. When a boost is to be employed, a CTV expansion is not required around the GTVPET+ volume, although an ITV/PTV expansion is required.

2. Post-Chemotherapy Clinical Target Volume (CTV)

For this study, the CTV should encompass the GTVtotal volume described above, plus any additional volume that may be required to account for uncertainty in disease localization due to variation in imaging, patient positioning, etc. Since the at-risk CT abnormality encompasses the PET-avid volume, this volume will almost always be larger than the GTVPET+ volume.

Delineation of the CTV requires consideration of the expected routes of disease spread, and the quality of the imaging. For example, in some circumstances it can be difficult to clearly rule out disease (e.g. in the aorto-pulmonary window) or not possible to exactly locate the CT/PET abnormality within an exact location in an axial image of the involved nodal space. Consideration of other clinical and imaging factors should guide decisions regarding whether to include or exclude such areas from the CTV.

The CTV expansion cannot be rigidly determined a priori as there can be uncertainties inherent with GTV delineation due to inaccuracies in matching patient positioning and the variable internal anatomy shifts that change with patient position between diagnostic and treatment positions. As a guideline, a margin of 1.0 cm above and below the GTVtotal is recommended. When boosting the PET-avid volume, it is not necessary to add a CTV expansion around the GTVPET+ volume (i.e. the CTVPET+ and the GTVPET+ are the same).

Uncommonly, normal nodal tissue may be included in the CTV if located between two anatomically close (i.e. within 5 cm) sites requiring RT that are going to be joined and treated as a single volume.

